 The secondary objectives are To assess the changes in vital signs during the exercise 	The secondary endpoints are: 1. Mean change from pre to 10 minutes: a. Pulse oximetry oxygen saturation (SpO2) b. Respiratory rate (RR)	Knowing the change in these biometric measures will assist in designing future investigations of patients at risk of
To assess change in vital signs at the end of the exercise	c. Blood pressure (BP) 2. Mean change from pre to end of VR session: a. SpO2 b. RR c. BP	delirium.
To assess the feasibility of VR-based cognitive stimulation exercises in older surgical patients.	using the ReCognitionVR-based cognitive exercise for 20 minutes by 70% of enrolled participants. using the ReCognitionVR-based cognitive exercise for 20 minutes by 70% of enrolled participants.	It is essential to know if participants can complete the exercise since an incomplete experience will prohibit the assessment of the other variables to be measured.
To determine the acceptability of VR-based cognitive stimulation exercises	the proportion of participants with a System Usability Scale (SUS) score >35.	Successful implementation depends on the acceptability of the intervention and is one of the main factors considered before adopting and implementing computerized cognitive software.

Page 3 of 21

OBJECTIVES	ENDPOINTS	JUSTIFICATION FOR ENDPOINTS
 To determine the accuracy of VR-games Technical difficulty with VR software 	 the proportion of participants who complete the game without any user errors. Number of attempts to complete the game. Number of software and device re-starts and re-sets. 	Accuracy is an essential variable in assessing the attention of the study subject. Attention is a prominent cognitive domain involved in delirium. Important to upgrade or incorporate advanced VR software.
Exploratory		
Exploratory outcome to report the episode of delirium	Confusion Assessment Method (CAM) tool (Appendix B) ⁶ or 4 A's Test score (Appendix C) ⁷ will be used to assess delirium.	Knowing the proportion of study subjects with new-onset delirium will assist in designing future investigations of patients at risk of delirium.

3. Background

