The study is a single-center, prospective assessment of the feasibility, acceptability, and usability of ReCognition VR -based simulated cognitive stimulation to improve attention and focus in surgical patients.

Sample size: We will enroll 30 participants: 15 participants who are ≥60 years of age with traditional orientation methods and 15 participants who are ≥60 years of age and receive ReCognitionVR-based cognitive exercises.

Justification of sample size: The study is a feasibility study expecting that 70% of participants in the study intervention group will complete 20 minutes of the ReCognitionVR-based exercise, where each group will be evaluated separately. Descriptive statistics will be used to summarize the findings; 15 participants in each group will be recruited. The intent is that this study will provide information for a larger, subsequent clinical trial of patients ≥60 years old at risk for delirium.

Data and measures to be taken:

The endpoints for this feasibility study are:

Primary Objective:

Safety/Tolerability: We will examine measures that can inform on the safety of the experience to be used in the subsequent clinical trial. The measures are:

- 1. Mean change from pre to 10 minutes of the ReCognition VR-based exercise in:
 - a. SpO2
 - b. RR
 - c. Blood pressure (Mean BP, Systolic BP, and Diastolic BP)
- 2. Mean change from pre to end of the ReCognition VR-based exercise in:
 - a. SpO2
 - b. RR
 - c. Blood pressure (Mean BP, Systolic BP, and Diastolic BP)

Secondary Objectives:

Feasibility: 70% of participants in each group will complete 20 minutes of use of the ReCognition VR-based software (a binary outcome).

Acceptability: We will measure the acceptability and usability of the experience based on the proportion of participants with a SUS score >35.

VR-games Accuracy: We will report on the proportion of participants who complete the game without any user errors and the number of attempts each participant uses to complete the game.

Page 6 of 21

Exploratory Objective:

Delirium: We will assess delirium using CAM tool⁶ or the 4 A's test⁷. Delirium is defined as any positive CAM Score or/and score of 4 or above on the 4 A's test for 72 hours after study interventions.

Accessing data from medical records:

Medical records of the potential study subjects will be reviewed for medical history for the inclusion and exclusion criteria described below in section 10.

Data analysis plan:

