All participants will be screened by the PI and clinical research staff, who have been trained in the clinical investigational plan, to determine if the potential participant is eligible for enrollment. The screening for potential participants will be from within the PI's department. Potential participants will be assigned a screening number which is recorded in an Excel sheet; all participants who receive the study intervention will be noted. All participants must meet eligibility criteria (and if not, which eligibility criteria were not met will be recorded); reasons for not meeting enrollment criteria or receiving study intervention will be recorded. No participants belonging to a vulnerable population will be enrolled.

During the informed consent process, the investigator or designee, who has been trained on the protocol, will explain the nature and scope of the intervention, potential risks, and benefits of participation and answer questions from the potential participants. All participants will sign and date the Institutional Review Board (IRB)/Ethics Committee (EC) approved informed consent form before any study-specific procedures are performed. In addition, the signed informed consent will be retained with the research records, and a copy will be given to the participant.

Medical records will be reviewed for screening.

12. Withdrawal of Subjects

A participant may discontinue his or her participation without giving a reason at any time during the study. For example, the PI may withdraw a participant due to failure to comply with study intervention requirements, or the participant is uncooperative or refuses to continue in the study intervention. The data from these participants will be retained in the study file and analyzed.

Participants will be withdrawn from the study if they do not receive any study interventions. At the moment of withdrawal, all data related to the participant will be removed from the corresponding Excel documents and waivers will be shredded.

13. Provisions to Protect the Privacy Interests of Subjects

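### The 70% feasibility target has three different denominators; two cannot be met with 15 VR patients among 30, and Section 12 removes never-starters from the third

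*Combined protocol and SAP*

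**What the plan says.** The 70% completion target appears three times, each time with a different denominator.

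- Section 2, Objectives and Endpoints table: "using the ReCognitionVR-based cognitive exercise for 20 minutes by 70% of enrolled participants".
- Section 4, Secondary Objectives: "Feasibility: 70% of participants in each group will complete 20 minutes of use of the ReCognition VR-based software (a binary outcome").
- Section 4, Justification of sample size: "70% of participants in the study intervention group will complete 20 minutes of the ReCognitionVR-based exercise".

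Section 4 also fixes the design: "We will enroll 30 participants: 15 participants who are ≥60 years of age with traditional orientation methods", with the other 15 receiving the VR exercise. Section 10 repeats the 15:15 split. Section 5 has participants enrolled and randomised after consent. Those in the VR arm receive the session once they are back from the operating room with a RASS score of 0.

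On patients who never start, Section 12 says "Participants will be withdrawn from the study if they do not receive any study interventions" and that at withdrawal "all data related to the participant will be removed from the corresponding Excel documents". Section 11 says that "reasons for not meeting enrollment criteria or receiving study intervention will be recorded".

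**The concern.** The three denominators are 30 people, 15 people in each of two arms, and 15 people in one arm. The control arm gets no VR, so it cannot contribute completers. Both formal endpoint statements (Sections 2 and 4) therefore appear to set a target that the design rules out. The workable version stands only in the sample size paragraph.

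The workable version has a second problem. A patient randomised to VR who never starts is a feasibility failure in the ordinary sense. If that patient's data are removed, the denominator shrinks and the completion rate rises. Section 11 points the other way by recording why someone did not receive the intervention, but nothing links that record to the endpoint.

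Feasibility is part of the stated hypothesis, and the results are meant to inform a later study in patients at risk of delirium. The share of patients who cannot start is information that study will need.

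**Working it through.** **Inputs.** Target 70%; 30 enrolled, 15 per arm; VR in one arm only (Sections 2, 4, 5 and 10). The plan gives no alpha, power, precision or dropout rate, so there is no sample size calculation to reproduce. The 15 per arm is asserted, and 15 + 15 = 30 is consistent.

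**Can each version be met?** Compare the completers needed, 0.70 × denominator rounded up, with the most that are possible.

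| Denominator | Needed | Most possible | Attainable? |
|---|---|---|---|
| All enrolled (30) | 0.70 × 30 = 21 | 15 (15/30 = 50%) | No |
| Each group: controls (15) | 0.70 × 15 = 10.5, so 11 | 0 (0/15 = 0%) | No |
| VR arm (15) | 0.70 × 15 = 10.5, so 11 | 15 | Yes |

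In the VR arm the smallest passing result is 11/15 = 73.3%, with a Clopper-Pearson 95% interval of 44.9% to 92.2%.

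**Effect of removing never-starters.** With c completers and k never-starters removed, the rate changes from c/15 to c/(15 − k). The fewest removals that bring a failing result to 70% are:

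| Completers | All 15 counted | Removals needed | After removal |
|---|---|---|---|
| 10 | 10/15 = 66.7% | 1 | 10/14 = 71.4% |
| 9 | 9/15 = 60.0% | 3 (9/13 = 69.2% falls short) | 9/12 = 75.0% |
| 8 | 8/15 = 53.3% | 4 | 8/11 = 72.7% |

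**Chance of meeting 70%.** The plan gives neither a start rate s nor a completion rate p among starters, so both are assumptions here. If never-starters count as failures, the chance is P(X ≥ 11) with X binomial(15, s × p). If they are deleted, it is the chance that at least 70% of m starters complete, averaged over m binomial(15, s). Each cell shows counted / deleted.

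| Start rate s | p = 70% | p = 80% | p = 90% |
|---|---|---|---|
| 100% | 51.5% / 51.5% | 83.6% / 83.6% | 98.7% / 98.7% |
| 90% | 29.4% / 51.4% | 58.5% / 81.9% | 86.1% / 98.1% |
| 80% | 13.7% / 52.0% | 32.2% / 81.0% | 58.5% / 97.6% |
| 70% | 5.1% / 54.3% | 13.7% / 81.2% | 29.4% / 97.2% |

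With deletion the result hardly responds to the start rate.

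**The case against.** **On the denominators.** One can read *enrolled* loosely as enrolled in the VR arm, and no sensible analyst would compute VR completion in controls. But Sections 4 and 10 use the word for all 30, Section 5 enrols before randomising, and the loose reading leaves *each group* unexplained. That phrase may come from the preliminary study in Section 3, where both groups used VR; this is only an inference. The objection lowers the practical risk but does not make the text right.

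**On Section 12.** There are three fair points.

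- The paragraph before the removal rule keeps and analyses data from participants who leave, do not comply or refuse to go on. Someone who declines before the first minute could fall under either rule. That ambiguity is real, but a patient who receives nothing is expressly covered by the removal rule.
- The Schedule of Activities puts randomisation at the pre-session time point on Day 1 and the RASS score at screening. On that schedule, a cancelled operation would be a screen failure rather than a VR-arm never-starter. This narrows the gap. It does not close it, because step 3 of Section 5 allows randomisation soon after consent, and a patient can still fail to start after the pre-session time point.
- Removal is ordered from the Excel documents, while data also go to REDCap, so complete loss is not certain. However, Section 8 says all study data are held in a spreadsheet, and no text says that the arm and the reason survive for this endpoint.

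**On size and remedy.** A single removal changes the outcome only at exactly 10 completers. Completion among starters, with uptake reported separately, would also be a legitimate analysis. The exact interval is an addition to a descriptive plan, and its absence is not an error. All three statements are correct.

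**Conclusion.** The concern holds. That two of the three versions cannot be met (ceilings of 50% overall and 0% in controls) follows from the 15:15 design and needs no assumption. The only workable version means at least 11/15.

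The Section 12 effect depends on at least one VR-arm patient not starting and on the removal rule being applied as written. The plan does not say how many never-starters to expect, so 66.7% against 71.4% is an illustration of direction and size, not a forecast. The bias can only favour feasibility.

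This should be fixed, but it does not threaten the trial. The endpoint is secondary and descriptive, no decision rule depends on it, and no type I error is involved.

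**What to change.** 1. **Sections 2 and 4:** use one definition throughout, namely participants randomised to VR who complete the 20-minute session, divided by all participants randomised to VR. Drop the references to enrolled participants and to each group from the feasibility endpoint.
2. **Target:** state that, with 15 in the VR arm, 70% means at least 11/15. Reporting it with an exact 95% CI is advisable but optional. Completion among starters can be shown beside it, provided that the number who did not start is given.
3. **Section 12:** do not remove a participant randomised to VR who never starts. Keep at least the assigned arm, a not-started flag and the reason, in line with Section 11, and count the participant as a non-completer. Say which of Section 12's two paragraphs covers a refusal before the session begins.

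The cost is a few lines of wording and one field in the log. The reported completion rate may come out lower, and an interval on 15 patients will look wide. The sample size and study procedures do not change.

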- Pain scores (using numeric pain rating scale tool)
- Safety adverse events

Identifier (or parts of)	Recorded	Disclosed	Comment
All elements of dates (except year) for dates	Yes	No	Necessary for complete data
directly related to an individual, including			analysis
patient names, birth date, admission date,			
discharge date, and date of death; and all			
ages over 89 and elements of dates			
(including year) indicative of such age			
Phone numbers; Fax numbers	Yes	No	Necessary to complete a
			questionnaire
Medical record numbers	Yes	No	Necessary to organize data
			collection

Page 12 of 21

Identifier (or parts of)	Recorded	Disclosed	Comment
Any other unique identifying number,	Yes	No	Virtual cognitive
characteristic, or code			interventions are frequently
			delivered

9. Data and Specimen Banking

No specimens will be obtained, stored, or banked in this study.

10. Study Population

This study will be a single-center study of older patients who underwent abdominal surgeries and will be conducted at Houston Methodist Hospital. We will enroll 30 patients scheduled to undergo abdominal surgery who are ≥60 years of age. The rationale for enrolling older patients is that older surgical patients are at high risk for the development of delirium.

A total of 30 patients will be prospectively enrolled. 15 patients will receive the standard of care / re-orientation technique, and 15 patients will receive ReCognitionVR-based cognitive exercises. All participants will be given post-use surveys to assess usability and acceptability outcomes.

Inclusion Criteria:

- 1. Patients ≥ 60 are scheduled to undergo the following abdominal surgeries (open or laparoscopic or robotic assisted) small bowel and large bowel surgery; cholecystectomy; Whipple procedure; pancreatectomy; splenectomy.
- 2. RASS Score 0

Exclusion Criteria:

- 1. Subjects with baseline cognitive impairment.
- 2. Person with active psychiatric disorders and being treated with medications, especially schizophrenia.
- 3. Person who is deaf or blind.
- 4. Person with an underlying cognitive disorder or associated phobias (e.g., claustrophobia).
- 5. Person participating in other clinical trials involving drugs, biologics, devices, or behavioral interventions.
- 6. Active seizure disorders.

11. Screening and Recruitment

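### The 70% completion rate is both the planning expectation and the feasibility criterion, with no interval planned, so one VR participant in 15 can flip the result on almost the same evidence

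*Combined protocol and SAP*

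**What the plan says.** The 70% figure appears three times, each time with a different population.

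- **Section 4, Justification of sample size**, as an expectation for the VR arm: "The study is a feasibility study expecting that 70% of participants in the study intervention group will complete 20 minutes". The same paragraph adds "where each group will be evaluated separately", "Descriptive statistics will be used to summarize the findings" and "15 participants in each group will be recruited".
- **Section 4, Secondary Objectives**, as the feasibility criterion for both arms: "70% of participants in each group will complete 20 minutes of use of the ReCognition VR-based software (a binary outcome".
- **Section 2, objectives and endpoints table**, as the feasibility endpoint for everyone enrolled: "using the ReCognitionVR-based cognitive exercise for 20 minutes by 70% of enrolled participants".

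Section 10 confirms that only half of the 30 are exposed: "15 patients will receive ReCognitionVR-based cognitive exercises".

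The text gives no lower rate that would count as unacceptable, no significance level or power, no precision target, and no confidence interval for any proportion. The data analysis plan in section 4 names means or medians for continuous variables and Chi-square or Fisher's exact tests for categorical ones.

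**The concern.** A criterion compared with a point estimate is informative only if the rate the team expects differs from the rate it must reach. Here they are the same number. An intervention that performs exactly as planned would therefore miss its own criterion about half the time, and the reader would have no interval to show how little a near miss differs from a near pass.

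At stake is what the trial can say about feasibility. Sections 2 and 4 state that the results will inform a later trial in patients at risk of delirium, and 70% completion is the only yardstick the protocol gives for feasibility. If the report says only that 70% was or was not reached, the next team inherits a label that can turn on one participant.

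**Working it through.** **Inputs.** Expected rate 70% (section 4, Justification of sample size). Criterion 70% (section 4, Secondary Objectives; section 2 table). VR arm n = 15 (sections 4 and 10).

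**1. Can 15 be reproduced?** No, because no significance level, power, null rate or precision target is given. For scale, the usual normal-approximation half-width at 70% is 1.96 × √(0.70 × 0.30 / 15) = 0.232, or ±23.2 points. By the same formula, ±20 points needs 21 participants and ±25 points needs 13.

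**2. The working count.** 0.70 × 15 = 10.5, so the smallest qualifying count is 11 (11/15 = 73.3%). Ten (10/15 = 66.7%) falls short.

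**3. Chance of meeting the criterion at the planned rate.** With X ~ Binomial(15, 0.70), the probabilities for X = 11 to 15 are:

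P(X ≥ 11) = 0.2186 + 0.1700 + 0.0916 + 0.0305 + 0.0047, which is 0.5155 before rounding of the terms.

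The criterion is missed with probability 1 − 0.5155 = 0.4845.

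**4. The same probability at other true rates.**

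| True completion rate | P(at least 11 of 15) |
|---|---|
| 55% | 12.0% |
| 60% | 21.7% |
| 65% | 35.2% |
| 70% | 51.5% |
| 75% | 68.7% |
| 80% | 83.6% |
| 85% | 93.8% |
| 90% | 98.7% |

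A true rate of about 79% is needed for an 80% chance of meeting the criterion.

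**5. Is n = 15 the cause?** Keep the true rate and the criterion both at 70% and vary n:

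| n | Count needed | P(criterion met) |
|---|---|---|
| 15 | 11 | 51.5% |
| 30 | 21 | 58.9% |
| 50 | 35 | 56.9% |
| 100 | 70 | 54.9% |
| 200 | 140 | 53.5% |

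The probability drifts back towards one half as n grows. The cause is that the expected rate equals the criterion.

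**6. What n = 15 does cause.** Exact (Clopper-Pearson) 95% limits are the 0.025 quantile of Beta(x, n − x + 1) and the 0.975 quantile of Beta(x + 1, n − x):

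| Completers | Proportion | Exact 95% CI |
|---|---|---|
| 10/15 | 66.7% | 38.4% to 88.2% |
| 11/15 | 73.3% | 44.9% to 92.2% |
| 14/15 | 93.3% | 68.1% to 99.8% |
| 15/15 | 100% | 78.2% to 100% |

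The intervals for 10 and 11 completers share the range 44.9% to 88.2%. That is 43.3 points of widths 49.8 (88.2 − 38.4) and 47.3 (92.2 − 44.9). One participant changes whether the criterion is met while the evidence barely moves.

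**7. The denominator.** If all 30 enrolled are counted, the most that can complete VR is 15/30 = 50%, so 70% cannot be reached. If each arm is counted, the control arm has no VR session to complete. Only the VR-arm reading works. Section 12 also withdraws participants who receive no intervention and removes their data, so the VR denominator could fall below 15. At a true rate of 70% the chance of meeting the criterion is then 58.4% with 14 (10 needed), 42.1% with 13 (10 needed) and 49.3% with 12 (9 needed).

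**The case against.** The strongest reply is that this is a small descriptive study whose results are to inform a larger one, so nothing is decided at 70%. Much of that stands. A reader might infer that the trial will formally declare the software not feasible, or that the next trial depends on the result. The documents contain no go/no-go rule and do not say this. The phrase "a binary outcome" most naturally describes each participant's completion, not a study-level pass or fail. But a descriptive aim is a reason to report the estimate with its uncertainty, and the endpoint is instead written as a threshold with no interval.

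A reader might also infer that 15 is too few and more patients are needed, or that a weak intervention would often meet the criterion. Neither is supported. The near-even chance persists at n = 200, and the criterion is met only 21.7% of the time at a true rate of 60% and 12.0% at 55%.

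A third reply is that completion was 100% in the preliminary study (section 3), so the true rate may be well above 70%. If it is 85% to 90%, the criterion would be met 93.8% to 98.7% of the time. But those were healthy volunteers, not patients just out of abdominal surgery, and the justification uses 70%.

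Finally, 10/15 might be accepted as roughly 70%. The chance at the planned rate then rises to 72.2%. A 21-point shift from an unstated rounding choice is itself a reason not to rest the result on the point estimate.

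**Conclusion.** The concern holds in a limited form. With expectation and criterion both at 70%, the chance of meeting the criterion on the point estimate is 51.5% at the planned rate. This assumes that all 15 VR participants are counted, that they complete independently, and that 10/15 is not rounded up. The cause is the coincidence of the two rates, not the sample size. The consequence of n = 15 is separate: the interval at the smallest qualifying count runs from 44.9% to 92.2%, and no interval is planned to show it. The denominator wording adds to the problem, since two of the three statements cannot be applied as written.

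Severity is minor to moderate. Feasibility is a secondary endpoint and the analysis is descriptive, but it is the only endpoint the sample size justification cites.

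**What to change.** 1. In the section 2 table and in section 4, define feasibility as the proportion of participants randomised to VR who complete 20 minutes. This replaces the wording that refers to each group and to all enrolled.
2. Use everyone randomised to VR as the denominator, counting those who never start as not completing. Reconcile section 12 with this, so that they are not removed from the count.
3. Add to the data analysis plan that this proportion is reported with an exact 95% CI.
4. State in the sample size justification the precision that 15 gives, for example about 45% to 92% at 11/15.
5. Describe 70% as a planning benchmark read together with the interval, not as a pass or fail on the point estimate. Requiring the lower limit to exceed 70% is not proposed: only 15/15 would satisfy it (14/15 has a lower limit of 68.1%).

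The cost is a few sentences and one interval. The criterion will look less decisive. No extra patients, visits or data are needed.
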